10.6.4 Statistical Methods for Safety Analyses

Safety results will be presented by Age Cohorts (12 to <18 years, 7 to <12 years, 3 to <7 years). Results of participants in the Expanded Cohorts will be reported separately from those in the Mini Cohorts, unless the same dose was given to both Mini and Expanded Cohorts within the age group.

Safety and tolerability will be assessed by clinical review of all relevant parameters, including AEs and laboratory parameters.

The analysis of safety parameters will follow a tiered approach ([Table 11](#)). The tiers differ with respect to the analyses that will be performed.

The first tier includes (1) AEs of elevated laboratory values that are reported as ECIs described in Section 9.3.7; (2) any AE; (2) a drug-related AE; (4) an SAE; (5) a serious and drug-related AE; and (6) an AE leading to discontinuation. Point estimates and 95% CIs will be provided for the proportion of participants with first tier AEs. The 95% CIs for the safety parameters will be estimated using the Clopper-Pearson method [Clopper, C. J. and Pearson, E. S 1934].

The second tier includes specific AEs by system organ class, vital signs, and standard laboratory safety tests at time points specified in the SoA. Point estimates will be provided for the proportion of participants with second tier AEs.

Missing safety laboratory or vital signs will be handled using the Data As Observed approach, that is, any missing value will be excluded from the analysis. The only exception is when a Baseline/Day 1 result is missing, this will be replaced with the latest pre-treatment result, if available.

The primary safety analysis will summarize the safety data for participants during the treatment period plus 14 days of follow-up.

Table 11 Analysis Strategy for Safety Parameters

Safety Endpoint	95% CI	Descriptive Statistics
AEs of elevated laboratory values that are reported as ECIs	X	X
Any AE	X	X
Any Serious AE	X	X
Any Drug-Related AE	X	X
Any Serious and Drug-Related AE	X	X
Discontinuation due to AE	X	X
Specific AEs or SOCs or PDLCs		X
Change from Baseline Results (laboratory vital signs)		X

95% confidence intervals will be calculated using the Clopper-Pearson method.
Note: AE = adverse event; CI = confidence interval; ECI = event of clinical interest; PDLC = pre-defined limits of change; SOC = System Organ Class; X = results will be posted.

10.6.5 Summaries of Baseline Characteristics, Demographics, and Other Analyses

10.6.5.1 Demographic and Baseline Characteristics

Baseline characteristics for all allocated and treated participants will be summarized by the use of descriptive statistics. No statistical hypothesis tests will be performed on these characteristics. The number and percentage of participants screened and allocated, and the primary reasons for screen failure and discontinuation will be displayed. Demographic variables (eg, age, gender, race, and GT subtype) and prior and concomitant therapies will be summarized using descriptive statistics for continuous or categorical variables, as

appropriate. Summary statistics for baseline efficacy measures such as HCV RNA will also be provided.

10.6.5.2 Growth

Height and weight will be compared to the normative population based on age as well as the mid-parental height. Summary statistics and changes from baseline at each time point during follow-up will be reported, where baseline is the start of the treatment period.

10.6.5.3 Viral Resistance Measurements

Viral resistance testing will focus on the entire NS3/4A and NS5A regions for all participants and for those who meet the virologic failure criteria (see Section 5.4.2.1.1).

10.6.5.4 Palatability and Acceptance Assessment

Each participant will rate the palatability and respond to questions on the acceptability of treatment with EBR/GZR on TW4 and TW8 of the study. This will be based on the FHS facial expression scale depicting various degrees of pleasure as an assessment of palatability (Section 5.4.2.2 and Section 9.10).

Descriptive statistics will be used to summarize the palatability and acceptability responses. Missing data will not be imputed, and the analyses will be based on observed data only. These analyses will be based on the FAS population.

10.7 Interim Analyses

To supplement the routine safety monitoring outlined in this protocol, the eDMC will monitor ongoing safety data and provide recommendations to ensure the safety of study participants and the integrity of the trial to the EOC (see Appendix 3 – Committees Structure – Executive Oversight Committee). HCV RNA data may be included as part of the reviews to allow for an assessment of benefit-risk. The eDMC will monitor the trial with suggested periodic reviews to occur approximately every 6 months. An internal statistician not otherwise connected with the trial will conduct the analyses and present results to the eDMC.

10.8 Multiplicity

There will be no multiplicity adjustments in the analysis of this trial.

10.9 Sample Size and Power Calculations

10.9.1 Sample Size and Power for PK Analyses

The precision of the estimates of EBR and GZR PK obtained from this study can be described in terms of the relative length of the 95% CIs expected for the given sample size and assumed variability. The calculations for AUC_{0-24} below are based on assumed true between-subject standard deviations (log-scale) of 0.452 and 0.731 for EBR and GZR, respectively, as observed in MK-5172 Protocol 059 (a Phase II/III non-randomized, unblinded, open-label study that evaluated the efficacy and safety of EBR/GZR in subjects with chronic HCV and advanced cirrhosis and hepatic insufficiency) and take into account

the sampling distribution of the observed sample variance as described in Wang et al [Wang, Y., et al 2012].

For the given sample size and assumed between-subject variability, there is ~80% probability that the 95% CI for the true GM AUC₀₋₂₄ will lie within the ranges shown in [Table 12](#), expressed relative to the observed GM. For example, given 22 participants in an Age Cohort, it is ~80% likely that the lower and upper bounds of the 95% CI for GZR AUC₀₋₂₄ will lie within 44% of the observed GM.

Table 12 Expected Precision (80% Likely) for Estimates of GZR and EBR AUC₀₋₂₄

Analyte	N	95% CI within X% of Observed GM
GZR	5	± 204%
	12	± 71%
	15	± 59%
	22	± 44%
EBR	5	± 99%
	12	± 40%
	15	± 33%
	22	± 25%

10.9.2 Sample Size and Power for Efficacy Analyses

The key efficacy objective will be assessed based on the proportion of participants achieving SVR₁₂, defined as HCV RNA <LLOQ 12 weeks after the end of all study therapy. This is an estimation study with no hypotheses. The expected response rate is ~95% based on previous EBR/GZR clinical trials. Treatment is expected to be similarly active in different Age Cohorts in either TN or TE pediatric participants with or without cirrhosis.

Efficacy results will be presented by Age Cohorts. Results of participants in the Expanded Cohorts will be reported separately from those in the Mini Cohorts, unless the same dose was given to both Mini and Expanded Cohorts within the age group. If all participants in an Age Cohort receive the same dose, then results of participants in Mini and Expanded Cohorts will be reported together. [Table 13](#) shows the 95% CIs for SVR₁₂ given varying assumptions of number of successes for 5, 12, 15, and 22 participants. Note that the intervals are not symmetric around the point estimate.

Table 13 Two-Sided 95% Confidence Intervals for SVR₁₂ (FAS Population)

	Observed Number of Successes (%)	Two-Sided 95% Confidence Interval [†]
N=5	3 (60.0%)	(14.7, 94.7)
	4 (80.0%)	(28.4, 99.5)
	5 (100.0%)	(47.8, 100.0)
N=12	9 (75.0%)	(42.8, 94.5)
	10 (83.3%)	(51.6, 97.9)
	11 (91.7%)	(61.5, 99.8)
	12 (100.0%)	(73.5, 100.0)
N=15	12 (80.0%)	(51.9, 95.7)
	13 (86.7%)	(59.5, 98.3)
	14 (93.3%)	(68.1, 99.8)
	15 (100.0%)	(78.2, 100.0)
N=22	18 (81.8%)	(59.7, 94.8)
	19 (86.4%)	(65.1, 97.1)
	20 (90.9%)	(70.8, 98.9)
	21 (95.5%)	(77.2, 99.9)
	22 (100.0%)	(84.6, 100.0)

FAS = Full Analysis Set
[†] Based on the two-tailed exact confidence interval for a binomial proportion (Clopper and Pearson) [Clopper, C. J. and Pearson, E. S 1934]

10.9.3 Sample Size and Power for Safety Analyses

The key safety objective of this study will be assessed by a review of the accumulated safety data. Certain safety endpoints of special interest have been identified in Section 10.6.3 of this document. Safety results will be presented by Age Cohorts. Results of participants in the Expanded Cohorts will be reported separately from those in the Mini Cohorts, unless the same dose was given to both Mini and Expanded Cohorts within the age group. If all participants in an Age Cohort received the same dose, then results of participants in Mini and Expanded Cohorts will be reported together.

The probability of observing at least one of a particular type of AE depends on the number of participants treated and the underlying percentage of participants with that AE in the study population. For instance, if the underlying incidence of a particular AE is 1% (1 of every 100 participants receiving the drug), there is a 20% chance of observing at least one AE of that type among 22 participants. If no AE of that type is observed among the 22 participants, this study will provide 95% confidence that the underlying percentage of participants with that particular AE is <15.4%.

The estimate of, and the upper bound of the 95% CI for, the underlying percentage of participants with an AE given various hypothetical observed number of participants with the AE are provided in [Table 14](#). These calculations are based on the exact binomial method proposed by Clopper and Pearson [Clopper, C. J. and Pearson, E. S 1934].

Table 14 Estimate of Incidence of AEs and 95% Upper Confidence Bound Based on Hypothetical Numbers of Participants with AEs

N	Hypothetical Number of Participants with an AE (Estimate of Incidence)	95% Upper Confidence Bound [†]
5	0 (0.0%)	52.2%
	1 (20.0%)	71.6%
12	0 (0.0%)	26.5%
	1 (8.3%)	38.5%
	2 (16.7%)	48.4%
15	0 (0.0%)	21.8%
	1 (6.7%)	31.9%
	2 (13.3%)	40.5%
	3 (20.0%)	48.1%
22	0 (0.0%)	15.4%
	1 (4.5%)	22.8%
	2 (9.1%)	29.2%
	3 (13.6%)	34.9%
	5 (22.7%)	45.4%

[†]Based on the two-tailed exact confidence interval for a binomial proportion (Clopper and Pearson) [Clopper, C. J. and Pearson, E. S 1934].

10.10 Subgroup Analyses

To assess the consistency of the response across various subgroups, the SVR₁₂ rate and associated 95% CIs will be estimated within each category of the following classification variables:

- Sex (female, male)
- GT (1a, 1 non-a, 4)
- Age (3 to <7 years, 7 to <12 years, 12 to <18 years)
- HCV RNA at baseline, ($\leq 800,000$ IU/mL, $> 800,000$ IU/mL; ≤ 2 million IU/mL, > 2 million IU/mL)
- Stage of fibrosis (Non-cirrhotic, Cirrhotic)
- Prior treatment history (TN, TE)
- Weight bands

The analyses by weight bands may be performed separately by age cohort and/or separately for Mini and Expanded Age Cohorts.

10.11 Compliance (Medication Adherence)

In this trial, the SMD will be used to monitor and document a participant's drug compliance. Data reported on the SMD will serve as the primary data for compliance analysis.

A day within the study will be considered an "On-Therapy" day if the participant takes the assigned treatment as noted in Section 7.5.1.

For a participant who is followed for the entire study period, the "Number of Days Should be on Therapy" is the total number of days from dosing to the last scheduled day for treatment administration for that participant. For a participant who discontinued from the study permanently, the "Number of Days Should be on Therapy" is the total number of days from dosing to the date of the last dose of study medication.

For each participant, percent compliance will then be calculated using the following formula:

$$\text{Percent Compliance} = \frac{\text{Number of Days on Therapy}}{\text{Number of Days Should be on Therapy}} \times 100$$

Summary statistics will be provided for percent compliance for the FAS population.

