8.1 Discontinuation of Study Treatment

Discontinuation of study treatment does not represent withdrawal from the study.

As certain data on clinical events beyond study treatment discontinuation may be important to the study, they must be collected through the participant's last scheduled follow-up, even if the participant has discontinued study treatment. Therefore, all participants who discontinue study treatment prior to completion of the protocol-specified treatment period will still continue to participate in the study as specified in Section 2 - SoA and Section 9.11.4 – Discontinued Participants Continuing to be Monitored in the Study.

Participants may discontinue study treatment at any time for any reason or be dropped from the study treatment at the discretion of the investigator should any untoward effect occur. In addition, a participant may be discontinued from study treatment by the investigator or the Sponsor if study treatment is inappropriate, the trial plan is violated, or for administrative and/or other safety reasons. Specific details regarding procedures to be performed at study treatment discontinuation are provided in Section 9.1.9 – Withdrawal/Discontinuation.

A participant must be discontinued from study treatment but continue to be monitored in the study for any of the following reasons:

- The participant or participant's legally acceptable representative requests to discontinue study treatment.
- The participant has a medical condition or personal circumstance which, in the opinion of the investigator and/or sponsor, placed the participant at unnecessary risk from continued administration of study treatment.
- Participant meets any HCV virologic failure criteria (see Section 5.4.2.1.1).
- The participant has a confirmed positive serum pregnancy test.
- A physician feels it is in the best interest of the participant to discontinue.
- ALT or AST increases to >500 IU/L and is confirmed with repeat test immediately.
- ALT or AST increases to $>3\times$ baseline and/or nadir, is >100 IU/L, and there is a simultaneous increase in total bilirubin $>2\times$ ULN and/or INR is increased from the baseline value and is >1.5 (unless the participant is on anticoagulation).
- Alkaline phosphatase increases to $>3\times$ ULN, there is a simultaneous increase in total bilirubin $>2\times$ ULN, and other causes of elevated alkaline phosphatase are excluded.

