- Alkaline phosphatase increases to $>5 \times$ ULN and other causes of elevated alkaline phosphatase are excluded.
- The participant has a life-threatening clinical or laboratory AE or an event that results in or prolongs an existing inpatient hospitalization that is assessed to be a study drug-related laboratory or clinical AE.

A participant **may** be discontinued from treatment but continue to be monitored in the study for any of the following reasons:

- SAE assessed by the physician investigator as possibly or probably related to study medication. Investigator may continue the participant in the trial, if it is deemed to be in the best interest of the participant to stay on the study treatment.
- Failure to comply with the dosing, evaluations, or other requirements of the trial.

For participants who are discontinued from study treatment but continue to be monitored in the trial, all visits and procedures, as outlined in the SoA, should be completed.

Participants may be allowed to begin study treatment again if deemed medically appropriate, upon consultation with the Sponsor.

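### Section 10.11 sets the compliance denominator by whether the child left the study, not by whether treatment was stopped; on its plain reading, full dosing to a Week 8 stop scores 67% or 100%.

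*Combined protocol and SAP*

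**What the plan says.** Section 10.11 defines percent compliance as days on therapy divided by the days the participant should have been on therapy, times 100. The denominator has two forms.

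- For a participant followed for the whole study, it "is the total number of days from dosing to the last scheduled day for treatment administration for that participant".
- The second form opens with "For a participant who discontinued from the study permanently" and ends the count at the date of the last dose.

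No separate form is given for a child who stops treatment early and stays in the study. The section closes: "Summary statistics will be provided for percent compliance for the FAS population".

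Section 8.1 separates the two events: "Discontinuation of study treatment does not represent withdrawal from the study". Its list of mandatory stops opens with "A participant must be discontinued from study treatment but continue to be monitored in the study for any of the following reasons", and for those children "all visits and procedures, as outlined in the SoA, should be completed". Section 9.11.4 sends early stoppers to an Early Discontinuation visit and then into follow-up. Section 8.1 also provides for a return to treatment: "Participants may be allowed to begin study treatment again if deemed medically appropriate", after consultation with the Sponsor.

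**The concern.** The protocol's default for an early treatment stop is that the child stays in the study. That is the case Section 10.11 does not name. On the plain reading, such a child falls under the first form and keeps the full scheduled denominator, so the days after a mandatory stop count as days not taken. A child with the same dosing who also leaves the study is counted only to the last dose.

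The FAS summary would then pool two quantities: the share of the planned course for those who stay, and the share of days up to the last dose for those who leave. Follow-up attendance after treatment, which says nothing about dosing, would decide which one applies. A child stopped as Section 8.1 requires, who then attends every visit, would look less compliant than an identical child who drops out. Section 5.4.2.2 describes adherence as necessary for SVR, so the summary should carry one meaning.

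**Working it through.** The plan states no compliance figure, so there is none to reproduce. The check applies the Section 10.11 formula directly.

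**Inputs**
- Planned course: 12 weeks (Section 5.1), dosed once daily (Section 3.2.1), so 12 × 7 = 84 days.
- Stop times: end of Week 8 (8 × 7 = 56 days) and end of Week 10 (10 × 7 = 70 days). These are illustrations. Section 3.2.3.2 places adult ALT/AST elevations around Weeks 8 to 10 but does not say how many would meet a stopping criterion.
- FAS size: about 56 (Section 10.1).
- Number of stops: not given in the documents; 1 to 3 is assumed.

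**Score for one child, plain reading**

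| Dosing | Followed to the end | Leaves the study |
|---|---|---|
| Every dose to a Week 8 stop | 56/84 = 66.7% | 56/56 = 100% |
| Every dose to a Week 10 stop | 70/84 = 83.3% | 70/70 = 100% |
| 50 of 56 doses to a Week 8 stop | 50/84 = 59.5% | 50/56 = 89.3% |

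Counting either the days taken or the planned days one day differently moves the 66.7% only within 64.7% (55/85) to 68.7% (57/83).

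**Effect on the FAS mean**, for a child who took every dose and stays, compared with counting to the last dose:
- Week 8: (100 − 66.7)/56 = 33.3/56 = 0.60 points per stop; for 1 to 3 stops, 0.60 to 1.79 points.
- Week 10: (100 − 83.3)/56 = 16.7/56 = 0.30 points per stop; for 1 to 3 stops, 0.30 to 0.89 points.

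Section 10.11 does not specify reporting by cohort. If that were done, one Week 8 stop would move the mean by 33.3/22 = 1.5 points in a group of 22, or 33.3/7 = 4.8 points in a Mini Age Cohort of 7.

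**Under a single rule tied to treatment status**
- To last dose for every permanent stop: 56/56 = 100% (or 50/56 = 89.3%), whether the child stays or leaves.
- Planned days for everyone: 56/84 = 66.7% in both cases.

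**A limit of the last-dose rule.** Take a child who abandons dosing at Week 4, is discontinued at Week 8 under the Section 8.1 reason "Failure to comply with the dosing, evaluations, or other requirements of the trial", and stays in follow-up. Section 10.11 on its plain reading gives 28/84 = 33%. The last-dose rule gives 28/28 = 100%.

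**The case against.** The strongest reply is that the first denominator is specific to the participant. Once a stop is required, it can be argued that no further treatment day is scheduled for that child, so full dosing to the stop would score about 100% in either follow-up status. A reader might infer that this reading is ruled out because it would leave the separate last-dose rule with nothing to do. The documents do not support that inference. In the example of dosing abandoned at Week 4, a schedule ending at the Week 8 stop gives 28/56 = 50%, while the last-dose rule gives 28/28 = 100%, so the two rules would still differ. What stands is that the shortened schedule is the less natural reading. Section 10.11 sets the last scheduled day against the date of the last dose in consecutive sentences, and nowhere says that a stop ends the schedule.

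A second reply is that the reference to leaving the study is loose wording for leaving treatment. Section 10.6.3 keeps the terms apart when it encourages children who stop treatment to remain for follow-up. If treatment was meant, the rewording below only makes that explicit.

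A third reply is that share of the planned course is a legitimate, conservative measure. That is correct, and planned days for everyone would also be consistent. The objection here is to mixing the two measures, not to either one.

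A fourth reply is that little depends on the percentage, because truncated courses can be seen elsewhere: Section 10.12 summarises days on therapy and Section 10.6.5.1 displays reasons for discontinuation. This also stands, and it limits the importance of the point.

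**Conclusion.** The concern holds as a minor defect in a stated rule, with medium confidence because of the alternative reading of the schedule. On the plain reading, identical dosing to a Week 8 stop scores 67% or 100% according to follow-up status. The 33-point gap describes one hypothetical child. On the FAS mean the effect is about 0.6 points per Week 8 stop and 0.3 per Week 10 stop, assuming every dose was taken up to the stop and about 56 participants. The number and timing of stops are assumptions.

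A reader might infer that the flaw reaches the main results. The documents do not support this. The percentage feeds only a descriptive summary and defines no threshold or population. The per-protocol PK set in Section 10.5.1 rests on its own judgement of dosing compliance up to Week 4. SVR12 and the safety analyses do not use the percentage. Nor do the documents make the last-dose denominator the only correct choice; what is needed is one rule based on treatment status.

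**What to change.** In Section 10.11, tie the denominator to treatment status.

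1. Apply the existing last-dose rule to every participant who permanently discontinued study treatment, whether or not the participant remains in the study.
2. Apply the scheduled-day rule to all others.
3. State how days off are counted for a child who stops and later restarts under Section 8.1, so that days in a required interruption are not scored as missed. Without this, restarters would keep the scheduled denominator and the same unfairness.
4. Because a last-dose denominator can hide abandoned dosing, report beside percent compliance the proportion completing the planned 12 weeks, with reasons for stopping.

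If the sponsor prefers planned days for everyone, that also removes the inconsistency, but days after a mandatory stop then count against the child and the summary should be labelled as share of the planned course.

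The cost is two reworded conditions, one sentence on restarts, a small programming change and one added summary line. The last-dose date and the reason for stopping are already collected under Section 9.11.4. The change can be made by amending Section 10.11 or recorded in the supplemental SAP that Section 10 provides for.
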